6.3.3 Treatment patterns

During follow-up, treatment patterns will be characterized in terms of dose, treatment duration, frequency of drug discontinuation, switching and use of add-on therapies. All patients included in the study will be deemed exposed (at least one inebilizumab treatment), but only those with complete 12-month follow-up will be considered in the evaluation of the treatment patterns as described below.

According to the product specifications, the 12-month follow-up will cover 3 potential inebilizumab administrations: initial intravenous (IV) infusion followed by a second

infusion 2 weeks later and a subsequent infusion 6 months after the first treatment (Figure 2A). The first and third infusion will be considered in defining inebilizumab treatment patterns.

Treatment duration will be the sum of days under inebilizumab exposure during the follow-up. Number of days under exposure will be calculated for the first and the third infusion as the difference between end date of inebilizumab exposure period and the administration/prescription/dispensation date (Figure 2B).

[figure not shown]
Inebilizumab complete **exposure period** will be assumed to last 180 days after drug administration/prescription/dispensation. The **end date of the exposure** period will be defined as the end of each inebilizumab exposure period within follow-up or the end date of follow-up if comes first (Figure 2B).

A patient will be considered to be in inebilizumab **continuous use** if no gap longer than 60 days occurs between the end date of the first inebilizumab exposure period and the beginning of the third (2B). **Temporary discontinuation** (intermittent users) will be defined in patients with gaps between inebilizumab exposure periods longer than 60 days but with a subsequent inebilizumab administration/prescription/dispensation during the follow-up. A patient will be defined as having **permanently discontinued** inebilizumab if no subsequent inebilizumab treatment is registered during the follow-up after the end date of the first inebilizumab exposure period.

Switchers will be a subgroup of patients who discontinue inebilizumab (temporarily or permanently) during the follow-up and have other NMOSD maintenance drug administered/ prescribed (Table 9) after the end date of inebilizumab exposure period (2C). The alternative NMOSD drugs will be described.

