The use of **add-on therapies** will be identified by administration/prescription/dispensation of other NMOSD maintenance or other immunosuppressive drug(s) (Table 9 and Table 10) during any of inebilizumab exposure period (2D). Corticosteroid pre-medication before inebilizumab infusion (used to reduce potential infusion reactions) will not be considered as an add-on therapy.

Figure 2 Inebilizumab treatment patterns

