6.7.2.2 Objective 2: Treatment patterns of inebilizumab

The number and proportion of patients in the overall study population receiving the drug, and by dose stratification, (below or above the recommended dose in the product characteristics [300 mg/IV infusion]) will be reported at each of the first, second, and third infusion. Additionally, the number and proportion of patients who change dose between the individual infusions as well as the time (in days) between the first and each subsequent treatment (regardless of dose) will be reported.

Inebilizumab treatment patterns, as described below, will be assessed in the period of 12 months from index date and only patients with a complete 12-month follow-up, regardless of inebilizumab discontinuation, will be considered.

The number and proportion of patients who experience the following treatment pattern related events will be reported separately for each of the events: continuous and discontinuous treatment, switching, use of add-on therapies, according to what is defined in [section 6.3.3](#). For all the events, the denominator consists of all patients exposed to inebilizumab and followed for the full 12-month period.

The median time to switching and the median time to use of add-on drugs will be described in the subgroups of switchers and patients using add-on therapies (as defined in [section 6.3.3](#)), respectively. For the subgroup of switchers (as defined in [section 6.3.3](#)), the time to switch will be calculated as the time from the index date until the first recorded start date of another NMOSD maintenance drug. For the subgroup of patients using add-on therapies (as defined in [section 6.3.3](#)), the time to add-on drug use will be calculated as the time from the index date until the first recorded start date of an add-on drug.

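### Section 6.3.3 always counts an early change of drug as add-on use and can never count a change after an on-time third infusion as a switch, and 6.7.2.2 can date a switch by an unrelated drug

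*Protocol*

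**What the plan says.** All the definitions are in Protocol section 6.3.3, and section 6.7.2.2 adopts them by reference.

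- **Exposure.** An exposure period "will be assumed to last 180 days after drug administration/prescription/dispensation", and it is cut at "the end of each inebilizumab exposure period within follow-up or the end date of follow-up if comes first". Of the three infusions expected in 12 months, only two open a period: "The first and third infusion will be considered in defining inebilizumab treatment patterns". The third is described as "a subsequent infusion 6 months after the first treatment".
- **Continuous use.** This applies "if no gap longer than 60 days occurs between the end date of the first inebilizumab exposure period and the beginning of the third".
- **Discontinuation.** It is temporary if the gap exceeds 60 days but inebilizumab is resumed, and permanent if no inebilizumab is recorded after the first exposure period ends. There is no rule for stopping after the third infusion.
- **Switchers.** They are a subset of the temporary or permanent discontinuers who "have other NMOSD maintenance drug administered/ prescribed (Table 9) after the end date of inebilizumab exposure period".
- **Add-on.** Its use "will be identified by administration/prescription/dispensation of other NMOSD maintenance or other immunosuppressive drug(s) (Table 9 and Table 10) during any of inebilizumab exposure period". Steroid pre-medication is excluded. No further inebilizumab is required.
- **Reporting.** Section 6.7.2.2 reports each event separately, with all exposed patients followed for the full 12 months as the denominator. Within switchers, time to switch is "the time from the index date until the first recorded start date of another NMOSD maintenance drug".

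**The concern.** Objective 2 asks how often patients switch and how often they use add-on therapy in the first 12 months. A reader will take add-on use to mean another drug taken alongside continuing inebilizumab. The rule does not measure that. It asks only whether another drug was recorded within 180 days of the first or third infusion, so a patient who has left inebilizumab for another drug falls into the same count as one on combined treatment.

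Switching has the opposite problem. It is open only to discontinuers, and discontinuation is judged only by what follows the first exposure period. Once the third infusion is given within the permitted gap, nothing that happens later can make the patient a switcher.

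The dating rule in 6.7.2.2 is not tied to the drug that made the patient a switcher. Table 9 includes oral steroids, so an earlier, unrelated course can set the switch date. The limitations in 6.9 mention none of this.

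**Working it through.** The protocol states no expected switching rate, add-on rate or time to switch, so there is no figure to reproduce. The check applies the written definitions to example patients.

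**Inputs (6.3.3):** exposure 180 days from the first and third infusions; permitted gap 60 days. **Assumed conversions:** 12 months = 365 days; third infusion at 6 months = about day 183 (range 181 to 184).

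**Derived limits**
- First exposure period ends: 0 + 180 = day 180.
- Latest third infusion still in continuous use: 180 + 60 = day 240.
- Second exposure period after a third infusion on day 183: 183 + 180 = day 363, leaving 365 − 363 = 2 days uncovered. For infusions on days 181 to 184 it ends on days 361 to 364, leaving 4 to 1 days.

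Condition 1 for a switch is being a discontinuer. Condition 2 is a Table 9 record after exposure ends. The last two columns take condition 2 as written (any record) and under a stricter reading (the drug must start after exposure ends).

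| Third infusion | Table 9 drug | Status | Add-on | Switch (record) | Switch (start) |
|---|---|---|---|---|---|
| none | from day 90, monthly to day 365 | permanent discontinuation | yes | yes | no |
| none | days 90 and 270 | permanent discontinuation | yes | yes | no |
| none | day 90 only | permanent discontinuation | yes | no | no |
| none | from day 200 | permanent discontinuation | no | yes | yes |
| day 183 | from day 270 | continuous | yes | no | no |
| day 240 | from day 300 | continuous | yes | no | no |
| day 183 | day 364 | continuous | no | no | no |
| day 250 | day 200 | temporary discontinuation (gap 70) | no | yes | yes |

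**Early change (first three rows).** Add-on every time. The patient is also a switcher only if a Table 9 drug is recorded after day 180, and never under the stricter reading.

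**Change after an on-time third infusion (rows five to seven).** Condition 1 fails, so this is never a switch under either reading. It is add-on unless the drug starts in the last few days, when it is neither.

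**Edge case.** A third infusion before day 180, such as day 175, meets the definitions of both continuous use and permanent discontinuation, because no inebilizumab follows the end of the first period. The bar on switching is therefore clean only for third infusions on days 181 to 240.

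**Time to switch.** Take a patient with no third infusion, an oral steroid on day 20 and a different Table 9 drug started on day 220. The day-220 drug makes the patient a switcher. The first recorded start of another maintenance drug is day 20, so 6.7.2.2 gives 20 days instead of 220.

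**The case against.** The strongest reply is that much of this is a defensible convention. The 180 days match the six-monthly maintenance interval given in section 4.1, so another immunosuppressant inside that window can fairly be called concomitant. A patient who stops after the first two infusions is still reported as permanently discontinued, so the abandonment is not hidden. The AESI analyses in 6.7.2.3 count patients as exposed regardless of discontinuation, so the switch label does not alter them. For a patient re-dosed on time, the 12-month window is itself the limit: the next infusion is due near day 363 (183 + 180), and with the 60-day gap that reaches about day 423. Figures 2C and 2D, which illustrate the two definitions, are not visible here, and the SAP may refine them.

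Most of this stands, and it limits the point. Three stronger inferences are not supported:

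- **That an early changer is never counted as a switcher.** Section 6.3.3 asks for a drug administered or prescribed after exposure ends, not started then, and 6.7.2.2 does not make the categories exclusive. An early changer with a later record and no third infusion is counted as both.
- **That time to switch is floored at day 181, in direct conflict with 6.7.2.2.** This needs the stricter reading. As written, 6.3.3 selects the switchers and 6.7.2.2 dates them, giving a sensible day 90 for the patient who changes on day 90. What remains is that the dating drug need not be the qualifying drug.
- **That about half of switches are lost.** One could compute 180/365 = 49%, and a median of day 273 against day 183. Those figures need both the stricter reading and an even spread of switch dates that the protocol does not give.

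The reply does not remove the add-on count for patients who never receive inebilizumab again, the structural zero for switching after an on-time third infusion, or the loose dating rule. An SAP that follows 6.3.3 inherits all three.

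**Conclusion.** The point holds as a limited defect in the definitions. Taking add-on to mean use alongside continuing inebilizumab, add-on is biased up, because every change of drug inside an exposure period enters it. Switching can be biased down. Changes after a third infusion on days 181 to 240 are always missed, and early changes are missed when no Table 9 record follows day 180. Median time to switch can be wrong in either reported population, overall or subgroup, wherever a switcher took another Table 9 drug earlier. No percentage can be attached, since neither the frequency nor the timing of switching is given. The day counts rest on 365 days of follow-up and a third infusion at about day 183. The AESI estimates are unaffected.

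**What to change.** 1. **Section 6.7.2.2.** Date the switch by the first post-index start of the specific drug whose record after exposure end made the patient a switcher. Exclude drugs already in use at index. The 6-month look-back for previous immunosuppressive therapy in section 6.1 can identify these.
2. **Section 6.3.3.** State that a record, not a start, after exposure end qualifies. Count a drug that qualifies as a switch only as a switch. Split add-on use by whether a further inebilizumab record follows, so that add-on without further inebilizumab is not read as combination therapy. The two-week infusion should not count as a further record, since 6.3.3 already sets it aside for treatment patterns. Keep Table 10 drugs and drugs continued from baseline in add-on, as now.
3. **Sections 6.3.3 and 6.9.** Report Table 9 starts after the third infusion with no later inebilizumab record as a separate undetermined category. State in the limitations that switching after the third infusion cannot be established within 12 months.

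The cost is wording and a small change to the classification program, with no new data. The downsides are that most changes after the third infusion will be undetermined and the add-on table gains a split. One weakness remains. An oral steroid started early and recorded again after day 180, in a patient with no third infusion, still qualifies as a switch, because Table 9 includes oral steroids. Listing the qualifying drug beside each switch count would make this visible, and 6.3.3 already plans to describe the alternative drugs.

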6 RESEARCH METHODS

6.1 Study Design

This will be a non-interventional multi-center cohort study of patients initiating inebilizumab conducted with secondary data sources in France, Germany, Italy, the Netherlands, and Spain. The study will be based on a cohort-event monitoring design to capture both drug utilization and selected safety outcomes in patients initiating inebilizumab. The proposed study design allows for an efficient initial descriptive evaluation of AESI.

The **study period** in individual countries will start on different dates, depending on the launching time of the drug (the earliest in the second quarter of 2022) (Table 1). The end of the study period will be also country-specific (the latest in December 2027) and will depend on the dates of data availability in individual data sources (different lag times and data release dates).

Table 1 Study periods, by country

	France	Germany	Italy	Netherlands	Spain
	SNDS/ NOMADMUS	GKV	RISM	PHARMO	SIDIAP
Launch date (quarter, year)	Q2, 2022	Q3, 2022	Q2 2023	Q3, 2023	Q2, 2023
Start of study period	May 2022	Aug 2022	May 2023	Aug 2023	May 2023
End of study period	Dec 2026	Dec 2026	Dec 2027	Dec 2026	Sep 2027
Study period duration (months)	57	54	56	41	53

Q2, 2nd quartile; Q3, 3rd quartile

The study population will be constituted by a cohort of adult female and male patients diagnosed with NMOSD with entry trigger by inebilizumab initiation.

[figure not shown]
The **index date** (Day 0) will be defined as the date of first treatment (date of administration/prescription/dispensation, depending on data available in selected data sources) (Figure 1). Patients initiating the treatment will be identified throughout the study period. After the index date, enrolled patients will be followed for 12 months or censored at end of study period or loss of follow-up (death, disenrollment/de-registering) whichever occurs first.

A **baseline period**, including any time from when data are available up to the index date, will be used to establish comorbidities and NMOSD-related clinical characteristics, whereas a short period of 6 months prior to or at index date will be used to determine previous immunosuppressive therapies.

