6.7.2 Planned Analyses

An eligible population will include all inebilizumab users identified during the study period in the selected data sources. From the eligible population, the population for analysis will be created by applying the study inclusion criteria, as defined in [section 6.2.1](#). The number and proportion of patients not included in the study for specific reasons will be presented in a STrengthening the Reporting of OBServational studies in Epidemiology (STROBE) (37) diagram.

All analyses will be conducted for the overall study population and in sub-groups of special interest: patients concomitantly receiving other immunosuppressive agents ([Table 9](#) and [Table 10](#) in Annex 3), and patients aged >65 years at the index date, if the sample size permits. Further details for the sample size required to conduct each of the analysis will be provided in the SAP.

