	6A551Z3 - Pheresis of Plasma, Multiple	ICD-10-PCS
	8-820 Therapeutic plasmapheresis	OPS

Abbreviations: ATC, Anatomical therapeutic chemical; ICD-10: 10th Revision of International Classification of Diseases; OPS, operation and procedure classification system, PCS, Procedure Coding System

* Only intravenous administrations

Table 9 NMOSD Maintenance Therapies

Name of Agent	Description	Coding
1. Oral Steroids	H02 - Corticosteroids for systemic use	ATC
2. Immunosuppressive therapies		
a. Azathioprine	L04AX01	ATC
b. Mitoxantrone	L01DB07	ATC
c. Mycophenolate Mofetil	L04AA06	ATC
d. Methotrexate	L01BA01; L04AX03	ATC
e. Cyclophosphamide	L01AA01	ATC
3. B-Cell Targeting Therapy (anti-CD20)		
a. Ocrelizumab	L04AA36 /L04AG08 from 2024	ATC
	6-00a.e Atezolizumab, parenteral	OPS
b. Ofatumumab	L04AA52/ L04AG12 from 2024	ATC
	6-006.4 Ofatumumab, parenteral	OPS
c. Rituximab	L01FA01	ATC
	6-001.h Rituximab, intravenously	OPS
	6-001.j Rituximab, subcutaneous	
4. Tocilizumab	L04AC07	ATC
	6-005.m Tocilizumab, intravenously	OPS
	6-005.n 8 Tocilizumab, subcutaneous	
5. Eculizumab	L04AA25/L04AJ01 from 2024	ATC
	6-003.h Eculizumab, parenteral	OPS
6. Satralizumab	L04AC19	ATC

Abbreviations: ATC, Anatomical therapeutic chemical; NMOSD, Neuromyelitis optica spectrum disorder; OPS, operation and procedure classification system

Table 10 Other Immunosuppressive Drugs of Interest

Name of Agent	Description	Coding
1. Interferon beta-1a and 1b	L03AB07; L03AB08	ATC
2. Dimethyl-fumarate	L04AX07; L04AX09	ATC
3. Alemtuzumab	L04AA34/L04AG06 from 2024	ATC
	6-001.0 Alemtuzumab, parenteral	OPS
4. Fingolimod	L04AA27/L04AE01 from 2024	ATC
5. Natalizumab	L04AA23/L04AG03 from 2024	ATC
	6-003.f Natalizumab, parenteral	OPS
6. Glatiramer acetate	L03AX13	ATC
7. Peginterferon beta-1a	L03AB13	ATC
8. Teriflunomide	L04AA31/L04AK02 from 2024	ATC
9. Bortezomib	L01XG01	ATC
	6-001.9 Bortezomib, parenteral	OPS
10. Cladribine	L01BB04; L04AA40	ATC
	6-00a.4 Cladribine, oral	OPS
11. Daclizumab	L04AC0	ATC
	6-009.9 Daclizumab, parenteral	OPS
12. Ozanimod	L04AA38/L04AE02 from 2024	ATC
13. Siponimod	L04AA42/L04AE03 from 2024	ATC
14. Tacrolimus	L04AD02	ATC

Abbreviations: ATC, Anatomical therapeutic chemical; OPS: operation and procedure classification system

Table 11 Pain Medication

Name of Agent	Description	Coding
1. Anti-inflammatory and antirheumatic drugs	M01	ATC
2. Topical products for joint and muscular pain	M02	ATC
3. Muscle relaxants	M03	ATC
4. Anesthetic drugs	N01	ATC
5. Analgesics	N02	ATC

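### The add-on rule in section 6.3.3 does not require the drug to be new, so the objective 2 add-on proportion mixes continued background therapy with therapy added to inebilizumab

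*Protocol*

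**What the plan says.** - **Event (section 6.3.3).** Add-on use "will be identified by administration/prescription/dispensation of other NMOSD maintenance or other immunosuppressive drug(s) (Table 9 and Table 10) during any of inebilizumab exposure period". One exclusion follows: "Corticosteroid pre-medication before inebilizumab infusion (used to reduce potential infusion reactions) will not be considered as an add-on therapy".
- **Window (section 6.3.3).** Each exposure period "will be assumed to last 180 days after drug administration/prescription/dispensation", and is cut at the end of follow-up if that comes first. The first and third infusions are the ones counted.
- **Proportion (section 6.7.2.2).** For every treatment-pattern event, "the denominator consists of all patients exposed to inebilizumab and followed for the full 12-month period". The events take their meaning from section 6.3.3.
- **Time to add-on (section 6.7.2.2).** This is "the time from the index date until the first recorded start date of an add-on drug".
- **Drug lists (Annex 3).** Table 9 includes azathioprine, mycophenolate mofetil and oral steroids, the last coded as "H02 - Corticosteroids for systemic use". Table 8 uses the same code for acute treatment, limited there to intravenous use.
- **Baseline (sections 6.1 and 6.3.2).** Under section 6.1, "a short period of 6 months prior to or at index date will be used to determine previous immunosuppressive therapies". Section 6.3.2 retrieves the Table 9 and Table 10 drugs over the 6 months before index to describe baseline maintenance therapy.
- **Subgroup (section 6.7.2).** All analyses are repeated in "patients concomitantly receiving other immunosuppressive agents", identified from the same Tables 9 and 10.

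**The concern.** An add-on is ordinarily a drug added to the one under study, and the protocol appears to mean this. Section 6.7.2.2 times add-on use to a start date. Section 6.9 groups augmentation with discontinuation and switching as treatment changes whose reasons cannot be captured. The rule in section 6.3.3 does not test for a start or a change. It tests only whether a listed drug was recorded while the patient was deemed exposed.

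The protocol expects patients on other immunosuppressants, since it makes them a subgroup of special interest. For someone who continues such a drug, the first refill after index satisfies the rule although nothing was added. An oral steroid taper after a relapse satisfies it as well, because only pre-medication is excluded.

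Use of add-on therapies is a named item of objective 2. Under this rule two different behaviours share one proportion, and the reported figure cannot be separated into its parts afterwards.

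**Working it through.** The protocol states no expected add-on proportion or time, so there is no figure to reproduce. The check compares the rules and then illustrates the size.

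**Step 1. Does any text require a new start?** Sections 6.3.2, 6.3.3, 6.7.2 and 6.7.2.2 were compared. None requires the drug to be absent before index. The pre-index Table 9 and Table 10 data are used to describe patients at baseline and are not linked to the add-on rule. By contrast, sections 6.2.1 and 6.3.1 do impose a 6-month no-prior-use condition on inebilizumab itself.

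**Step 2. How much time is open to a qualifying record?** Two counted exposure periods of 180 days give 2 x 180 = 360 of 365 days for a continuous user. A patient who stops after the first period still has 180 days. A continuing drug refilled every 30 or 90 days will be recorded in either window.

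**Step 3. Proportion (assumed inputs).** Let b be the share who continue a Table 9 or 10 agent, and let 5% of the remainder truly add one. Continuing users are assumed to add nothing further.
- Reported share = b + (1 - b) x 0.05
- True share of the cohort = (1 - b) x 0.05

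| b | Reported | True |
|---|---|---|
| 20% | 0.20 + 0.80 x 0.05 = 24% | 0.80 x 0.05 = 4% |
| 60% | 0.60 + 0.40 x 0.05 = 62% | 0.40 x 0.05 = 2% |

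A second set of assumptions lets new starts occur in a share a of all patients, independently of background therapy. Reported share = 1 - (1 - a)(1 - b), and the true share is a.

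| b | a = 5% | a = 10% |
|---|---|---|
| 10% | 14.5% | 19% |
| 30% | 33.5% | 37% |
| 50% | 52.5% | 55% |

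**Step 4. Time to add-on, under each reading of the start date.**
- *First qualifying record after index.* For a continuing user this is the next refill, at most one refill interval away. If refills fall evenly, the mean wait is 30/2 = 15 days or 90/2 = 45 days. With the second set of assumptions, and true new starts spread evenly over days 1-360, simulation gives an overall median of 16-27 days with 30-day refills and 46-70 days with 90-day refills. Among true new starts alone the median is about 180 days.
- *True start of the drug.* For a continuing user this lies before the index date, so the time is negative, yet the patient still counts in the proportion.

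**Step 5. Subgroup on other immunosuppressants.** The same two tables define both the subgroup and the event, but section 6.7.2 does not say when concomitance is judged.
- *Judged during exposure:* every member has a qualifying record, apart from the pre-medication exclusion, so add-on use is 100%.
- *Judged at index:* members who have no later record of a listed drug during exposure are not add-on users. The proportion is strongly inflated but need not reach 100%.

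**The case against.** - **The SAP may settle it.** Section 6.7.1 promises full variable definitions in the SAP, which is not at hand, and a no-prior-record rule could be seen as operational detail. This stands only in part. Section 6.3.3 fixes the rule and section 6.7.2.2 refers back to it. Where the protocol defers a definition, as for treatment indication, relapses and incident AESI, it says so.
- **Figure 2 is not visible.** Its panel on add-on therapies might show a drug started during exposure. That cannot be checked, but the written rule contains no such condition.
- **Background therapy is reported elsewhere.** Objective 1 will show pre-index use beside the add-on figure. This helps a reader, but a marginal baseline share does not reveal which add-on users were continuing.
- **Stronger inferences go too far.** A reader might infer that median time to add-on simply becomes the refill interval of old drugs. That depends on how the start date is read, and on refill-type records; the Italian registry is described as recording treatments, with no mention of refills. A reader might also infer that add-on use in the subgroup is 100% by construction, but the protocol does not give the window this needs. Nor is objective 2 emptied of information: the add-on rule does not touch duration, dosing, discontinuation or switching. That readers would conclude inebilizumab often needs supplementing is conjecture about a descriptive study without a comparator.

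**Conclusion.** The point holds for the proportion. As written, section 6.3.3 counts continued background therapy as add-on use, and this follows from the text without any assumption. For time to add-on, neither reading of the start date gives a usable value for continuing users: one yields a refill date, the other a negative time. In the subgroup, strong inflation is to be expected; 100% follows only if concomitance is judged during exposure.

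The size is not known. The 24-62% reported against 4-2% true rests wholly on an assumed 20-60% continuing and 5% of the rest adding. The 14.5-55% range and the median times rest on the second set of assumptions. None of these inputs comes from the protocol.

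This should be changed, because it alters a named objective 2 result. It is a descriptive measure, so nothing beyond the add-on results depends on it.

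**What to change.** 1. **Section 6.3.3, definition.** Define add-on as the first record, on or after the index date and during an exposure period, of a Table 9 or Table 10 agent with no record of that agent in the 6 months strictly before the index date. The window in section 6.1 includes the index date; using it unchanged would class a drug newly started that day as continued. The pre-medication exclusion stays.
2. **Section 6.3.3, continued therapy.** Report agents recorded both before and after index separately, as continued concomitant therapy.
3. **Section 6.3.3, steroids.** Report oral steroid courses that follow a recorded acute treatment separately from add-on.
4. **Section 6.7.2.2.** Restrict time to add-on to newly started agents.

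The cost is a few sentences and one extra table row; the pre-index drug data are already extracted. Reported add-on use will be lower, and an agent restarted after a gap of more than 6 months will count as new.
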